such that  $\text{RR} = e^\beta$  where  $\beta$  is the coefficient for the Restrictive assigned strategy (versus Liberal assigned strategy) from the log-binomial model for the primary endpoint. If superiority of one of the two transfusion

strategies is not demonstrated through the primary hypothesis test, a second hypothesis test of interest is the non-inferiority of the Restrictive Strategy compared to the Liberal strategy. Setting the non-inferior margin to a 15% relative increase, we will conduct the following one-sided non-inferiority hypothesis test with  $\alpha=0.025$ :

$H_0: RR \geq 1.15$  versus  $H_A: RR < 1.15$  using a one-sided  $\alpha$ -level=0.025.

With this test, rejecting the null hypothesis leads to the conclusion that the restrictive arm is non-inferior to the liberal arm. This is equivalent to the demonstrating that the entire 95% confidence interval for the estimated RR is  $< 1.15$ .

Among all patients with 30-day outcome data, the observed proportion of patients who experience the primary endpoint in each assigned group, the risk ratio (Restrictive versus Liberal) and 95% confidence interval, the risk difference (Restrictive – Liberal) and 95% confidence interval will be calculated and presented. See Table 2. We will determine whether this estimated 95% confidence interval for the RR includes 1.00 to assess superiority and whether it is  $< 1.15$  to assess non-inferiority of the Restrictive strategy. All available data from randomization through 30 days will be used to identify death and MI outcomes; for patients with incomplete follow-up, we assume that no event occurred after the time of last contact.

Kaplan-Meier methods will be used to display the cumulative risk of the primary endpoint over the 30-day post-randomization follow-up period for all randomized patients stratified by assigned treatment group (Figure 3a). For the Kaplan-Meier analyses, follow-up will be censored at the time of withdrawal, lost-to-follow-up, or 30 days, and a log-rank statistic will be used to compare the two curves. The estimated risks at 30-days and the risk difference and 95% confidence interval at 30-days will be presented.

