## **Analysis of Secondary and Other Outcomes**

All of the secondary outcomes and most of the tertiary outcomes are dichotomous endpoints (i.e. presence/absence of an event during the 30-day study period). The pre-defined secondary outcomes are: 1) all-cause mortality within 30 days; 2) myocardial reinfarction within 30 days; and 3) the composite outcome of all-cause mortality, nonfatal myocardial reinfarction, ischemia driven unscheduled coronary revascularization (percutaneous coronary intervention or coronary artery bypass grafting), or readmission to the hospital for ischemic cardiac diagnosis within 30 days. Other dichotomous outcomes include: 1) all-cause mortality, nonfatal myocardial reinfarction, and unstable angina (i.e. acute coronary syndrome) 2) ischemia driven unscheduled coronary revascularization within 30-days; 3) readmission to the hospital for ischemic cardiac diagnosis, 4) congestive heart failure within 30 days; 5) unscheduled readmission to

hospital for any reason within 30 days; 6) each of the individual cardiovascular outcomes of stroke, pulmonary embolism or deep venous thrombosis, bleeding, and cardiac death within 30 days; 7) each of the individual infectious outcomes of pneumonia and blood stream infections within 30 days.

For each of the dichotomous endpoints listed above, the observed proportion of patients who experience the endpoint in each assigned group, the risk ratio (Restrictive versus Liberal) and 95% confidence interval, the risk difference (Restrictive – Liberal) and 95% confidence intervals will be calculated and presented (Table 2). Superiority of either transfusion strategy for each endpoint will first be evaluated using a two-sided test with  $\alpha=0.05$ . If superiority is not detected, the non-inferiority of the Restrictive strategy will be assessed using a 15% relative non-inferiority margin; that is, the Restrictive strategy will be deemed non-inferior for a given dichotomous endpoint when the entire 95% confidence interval for the estimated RR is  $< 1.15$ . For the 30-day dichotomous outcomes, all available data from randomization through 30 days will be used to identify outcomes. Patients with incomplete follow-up will be assumed to have no event after the time of last contact for these analyses.

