The length of hospital stay from randomization to discharge and the number of days in the ICU from randomization to discharge will be described as a mean (sd) or median (first and third quartile) in each assigned group and the difference will be analyzed using non-parametric Wilcoxon rank sum tests (see for example, Table 3). The mean (sd) or median (first and third quartile) will be presented for the EQ-5D utility index value and the EQ-5D Health Today score at 30 days post-randomization, and the difference will be tested based on t-tests or the Wilcoxon rank sum test depending on the distribution of the scores. The proportion of patients who report no problems with each of the 5 individual components of the EQ-5D (Mobility, Self-Care, Usual Activities, Pain/Discomfort, Anxiety/Depression) will be presented stratified by assigned treatment group (Table 3).

The cumulative risk of all-cause mortality through 180-day post-randomization will be estimated using Kaplan-Meier methods for all randomized patients stratified by assigned treatment group (Figure 3b). For the time-to-event analyses, follow-up will be censored at the time of withdrawal, lost-to-follow-up, or 180 days. The estimated risk at 30 days and at 180 days for each treatment group will be presented, and a log-rank statistic will be used to test the hypothesis that the mortality risk over the 180-days is equivalent in the two assigned treatment groups. The estimated risk difference (Restrictive – Liberal) and 95% confidence interval will be presented for cumulative mortality risk at 30 days and at 180 days. If neither strategy is found to be superior based on the log rank test and the 95% confidence interval for the estimated risk difference (RD) at 180-days includes 1.0, the 95% confidence interval for the 180-day mortality risk difference will be assessed using a non-inferiority margin equal to an absolute difference of

3.0%. Thus, if the entire estimated 95% confidence for the 180-day mortality RD is <3.0%, the Restrictive strategy will be considered non-inferior to the Liberal Strategy.

Missing data will not be imputed for the analyses of the secondary and tertiary hypotheses unless critical issues are noted while investigating the missing 30-day primary outcome data.

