**Table 2: MINT Trial Outcomes**

Characteristic	Cumulative Events at 30 days (Patient-Level)				
	Restrictive (N=)	Liberal (N=)	Risk Difference* (95% CI)	Risk Ratio* (95% CI)	p-value
Primary Outcome (at 30 days)					
All-cause mortality/adjudicated myocardial infarction (MI), n (%)					
Secondary Outcome (at 30 days)					
All-cause mortality, n (%)					
Adjudicated myocardial infarction, n (%)					
All-cause mortality, adjudicated MI, ischemia driven unscheduled revascularization, unscheduled readmission to the hospital for ischemic cardiac diagnosis, n (%)					
Other Outcome (at 30 days)					
All-cause mortality, adjudicated non-fatal MI, unstable angina, n (%)					
Ischemia driven unscheduled revascularization, n (%)					
Unscheduled readmission to the hospital for ischemic cardiac diagnosis, n (%)					
Heart Failure, n (%)					
Unscheduled readmission to hospital for any reason, n (%)					
Stroke, n (%)					
Pulmonary embolism or deep vein thrombosis, n (%)					
Bleeding event, n (%)					
Cardiac Death, n (%)					
Pneumonia or bacteremia, n (%)					

\* Risk Difference = Restrictive - Liberal for event outcomes

Risk Ratio = Restrictive / Liberal for event outcomes

Restrictive is considered non-inferior to Liberal if the upper bound of the Risk Ratio 95% Confidence Interval is <1.15

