**Table 3: MINT Additional Outcomes**

	Restrictive (N=)	Liberal (N=)	Mean Difference* (95% CI)	p-value		
Outcomes						
Length of hospital stay, number of days, mean (sd)						
Length of stay in the ICU, number of days, mean (sd)						
EuroQol 5D at 30-days						
EuroQol 5D results, n (%)						
EQ-5D Utility Index, mean (sd)						
EQ-5D Health Today, mean (sd)						
	Restrictive (N=)	Liberal (N=)	Risk Difference* (95% CI)	Risk Ratio* (95% CI)	p-value	
No problems identified with:						
EQ-5D Mobility, n (%)						
EQ-5D Self-Care, n (%)						
EQ-5D Usual Activities, n (%)						
EQ-5D Pain/Discomfort, n (%)						
EQ-5D Anxiety/Depression, n (%)						
	Restrictive (N=)	Liberal (N=)	Restrictive K-M Estimate at 180 days	Liberal K-M Estimate at 180 days	Risk Difference** (95% CI)	p-value
All-cause mortality at 180 days, n (%)						

\* Mean difference = Restrictive - Liberal

Risk Difference = Restrictive - Liberal for event outcomes

Risk Ratio = Restrictive / Liberal for event outcomes

\*\* For 180-day all-cause mortality Restrictive is considered non-inferior to Liberal if the upper bound of the Risk Difference 95% Confidence Interval is <3.0%

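### The 180-day mortality non-inferiority rule tests the risk-difference interval against 1.0, the no-difference value of a ratio, when it should be 0

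*SAP*

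**What the plan says.** The rule is in SAP section 6, Analysis of Secondary and Other Outcomes, in the paragraph on mortality through 180 days.

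- **Test.** A log-rank statistic tests whether "the mortality risk over the 180-days is equivalent in the two assigned treatment groups".
- **Contrast.** The effect measure is a difference in Kaplan-Meier risks, restrictive minus liberal. The notes to Table 3 repeat this: "Risk Difference = Restrictive - Liberal for event outcomes". Protocol F4, 4.d also specifies an absolute difference at 180 days, with no non-inferiority step.
- **Condition for assessing non-inferiority.** Neither strategy is superior by the log-rank test, and "the 95% confidence interval for the estimated risk difference (RD) at 180-days includes 1.0".
- **Criterion.** Restrictive is declared non-inferior "if the entire estimated 95% confidence for the 180-day mortality RD is <3.0"%, an absolute margin.

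For the primary endpoint the SAP uses the value 1.00 with a ratio: "We will determine whether this estimated 95% confidence interval for the RR includes 1.00 to assess superiority".

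**The concern.** A difference between two equal risks is 0. The value 1.0 is the no-difference point of a risk ratio, and the SAP defines no 180-day risk ratio. The numeral was probably carried over from the risk-ratio wording of the primary analysis.

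At stake is whether the pre-specified rule for a mortality outcome can be applied as written. If it cannot, someone must reinterpret it at analysis. In an open-label trial, a non-inferiority claim on mortality that depends on such a reinterpretation is open to dispute.

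**Working it through.** **Inputs**

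- 3500 patients allocated 1:1, so 1750 per arm (SAP, Trial Design and Interim Monitoring Plan). As a variant, 3324 analyzable, so 1662 per arm (SAP section 4; that figure refers to 30-day data).
- Two-sided 95% intervals; margin 3.0 percentage points.
- The documents give no 180-day mortality. I assume 10% to 30%, a normal approximation and no censoring. The true difference is 0 at first and then varied.

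**Step 1: the no-difference value.** With the same risk p in both arms, p - p = 0 and p / p = 1. Only a ratio has 1.0 as its no-difference value.

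**Step 2: the condition read as a proportion.** An interval containing 1.0 has an upper limit of at least 1.0, that is 100%. The criterion requires an upper limit below 0.03. Both cannot hold, so non-inferiority could never be declared. With 1750 per arm the half-width is only about 0.020 to 0.030 for 10% to 30% mortality, so the condition would not be met by any realistic result.

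**Step 3: the condition read as percentage points.** The interval must contain a 1-point excess in the restrictive arm.

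*Example.* Restrictive 19%, liberal 21%, 1750 per arm:

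- SE = sqrt(0.19 × 0.81/1750 + 0.21 × 0.79/1750) = 0.01352
- Interval: -2.0 ± 1.96 × 1.352 = -4.65 to +0.65 points; z = -1.48, p = 0.139

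This interval contains 0 and lies wholly below 3.0, so a condition at 0 gives non-inferiority. It excludes 1.0 on either reading, so the rule as written does not. By contrast, 20% in both arms gives -2.65 to +2.65 points, which passes the percentage-point condition.

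**Step 4: how often the percentage-point condition matters.** Let SE = 100 × sqrt(2p(1-p)/n), h = 1.96 × SE, and x be the observed difference in points. The log-rank condition is approximated by |x| ≤ h. Then:

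- Condition at 0: P(-h ≤ x < min(h, 3-h))
- Condition at +1 point: P(1-h ≤ x < min(h, 3-h))

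With 1750 per arm and a true difference of 0:

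| Mortality | h (points) | Declared, condition at 0 | Declared, condition at +1 | Share surviving |
|---|---|---|---|---|
| 10% | 1.99 | 81.6% | 67.6% | 82.8% |
| 15% | 2.37 | 67.5% | 57.1% | 84.6% |
| 20% | 2.65 | 57.7% | 49.1% | 85.1% |
| 25% | 2.87 | 51.1% | 43.5% | 85.1% |
| 30% | 3.04 | 46.6% | 39.6% | 85.1% |

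So about 15-17% of declarations are lost, and the same with 1662 per arm (83.2% to 85.1% survive). The lost results have x between -h and 1-h; at 20% mortality that is -2.65 to -1.65 points, all favouring restrictive.

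**Step 5: dependence on the true difference.** Same formulas, 1750 per arm, over 10% to 30% mortality:

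| True difference (points) | Share of declarations lost |
|---|---|
| +2 | about 1-4% |
| +1 | about 5-8% |
| 0 | about 15-17% |
| -1 | about 25-42% |
| -2 | about 37-68% |

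**The case against.** The strongest reply is that this is a one-character slip whose meaning is plain. The clause concerns the case where neither strategy is superior, it names a risk difference, and the log-rank hypothesis beside it is equal risk. Only 0 fits. The outcome is tertiary aim 10. That stands, and it limits the weight of the point. It does not make the printed threshold right.

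A second reply is that the criterion also appears without the condition. The Table 3 footnote reads "Restrictive is considered non-inferior to Liberal if the upper bound of the Risk Difference 95% Confidence Interval is <3.0"%, and the interval is reported in any case. But the unconditioned sentence in the text is drawn as a consequence of the conditional one before it, so it does not replace it. The footnote is table shorthand. Table 2 does the same, with "Restrictive is considered non-inferior to Liberal if the upper bound of the Risk Ratio 95% Confidence Interval is <1.15", although the text there also has a prior step: "If superiority is not detected, the non-inferiority of the Restrictive strategy will be assessed using a 15% relative non-inferiority margin". I do not count the footnote as a separate error.

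A third reply is that the percentage-point reading is unlikely, since the margin carries a percent sign and the 1.0 does not, and that 15-17% holds only for a true difference of 0. Both are fair. The loss is therefore shown as a range, and the conclusion rests on the wrong value, not on that percentage.

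Finally, it is tempting to say that with 0 in the condition, text and footnote differ only where restrictive is already superior. That holds only with the log-rank test approximated by the day-180 difference, and with mortality above about 5.4% at 1750 per arm (below that, 2h < 3 and an interval could lie wholly between 0 and 3.0). The log-rank test compares whole curves, so an early difference that narrows by day 180 could separate the two.

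**Conclusion.** The concern holds. The threshold in the 180-day mortality rule is wrong as written, and neither choice of units repairs it: as a proportion the rule blocks every declaration of non-inferiority, and as percentage points it blocks some of the non-significant results that favour restrictive. The size of the second effect depends on mortality and true-difference values that the documents do not give.

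The reach is narrow. The risk difference, its interval, the log-rank test, the 3.0% margin and the risk-ratio criteria for the primary and secondary outcomes are unaffected. It should be fixed because it is a definite error in a pre-specified decision rule on mortality.

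**What to change.** In the 180-day mortality paragraph of SAP section 6, Analysis of Secondary and Other Outcomes, change the value that the risk-difference interval must contain from 1.0 to 0, as a dated correction before the 180-day results are analysed. The Table 3 footnote needs no separate correction. A short note under both Table 2 and Table 3, that the margin applies only when superiority is not shown, is optional.

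The cost is one numeral in the text. Data collection, sample size, estimates and the primary analysis do not change.

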## Subgroup Analyses

Subgroup analyses will be performed based on the following baseline factors: STEMI and NSTEMI, MI types 1 and 2, baseline hemoglobin level (<8, 8-8.9, ≥9 g/dL), revascularization for treatment of index MI prior to randomization (yes, no), acute anemia (acute anemia, chronic anemia), sex (male, female), age (<60, 60-69, 70-79, ≥80 years), heart failure (defined as history of congestive heart failure, congestive heart failure during the index hospitalization prior to randomization and/or left ventricular ejection fraction < 45%: yes, no), renal function (renal dialysis during index hospitalization prior to randomization, no dialysis and eGFR <30, no dialysis and eGFR 30-59, no dialysis and eGFR ≥ 60 mL/mi/1.73m^2) based on the CKD-EPI formula without race, and diabetes mellitus (diabetes mellitus treated with medication: yes, no). For participants from sites in the United States, Canada, New Zealand and Australia, we will also consider Race (White, Black, Non-White and Non-Black Race) and Hispanic ethnicity (yes, no). Participants from the European Union (EU) and Brazil are excluded from these analyses because race and ethnicity were not collected in the EU sites, and these concepts are challenging to define in Brazil.

The proportion of patients with a primary endpoint within 30 days will be reported for each assigned treatment group within each pre-defined subgroup. If subgroup categories are too small for meaningful inference, we will collapse or eliminate categories. The risk ratio (Restrictive / Liberal), 95% confidence interval and significance-level will be reported with a forest plot (Figures 4a and 4b). For each subgroup variable, a log-binomial regression model including subgroup variable, treatment assignment and the interaction between the subgroup variable and treatment assignment will be created, and the significance of the interaction term will be used to test whether the treatment effect is significantly modified by the designated subgroup variable.

$$\text{Ln}(p_i) = \beta_0 + \beta_1 \text{Subgroup}_i + \beta_2 \text{Restrictive}_i + \beta_3 \text{Subgroup}_i * \text{Restrictive}_i + \varepsilon_i$$

where  $p_i = \text{Prob}(\text{Primary Endpoint}=1 \mid \text{Participant Assigned Treatment and Subgroup})$ ,  
 $i = \text{participant}$ ;

The focus of the subgroup analyses in the MINT trial is for descriptive purposes. When applicable, continuous versions of the subgroup variable will be considered for the regression models, and we will

explore the existence of inflection points for treatment effectiveness. Subgroup analyses may be examined for secondary and other outcomes utilizing similar methods. For 6-month mortality, Cox proportional hazards regression models will be created with the same covariates to test whether the effect of the randomized transfusion strategy for 6-month mortality varies significantly according to the pre-specified subgroup variables.

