Event rates, the relative risk and the absolute difference between transfusions strategy groups for the dichotomous secondary and tertiary outcomes will be calculated with their 95% confidence intervals using log-binomial regression methods accounting for clinical site with random effects. The length of hospital stay from randomization and from admission will be analyzed using non-parametric Wilcoxon

rank sum tests, and long-term mortality will be analyzed with Kaplan-Meier methods and the log rank statistic. The Kaplan-Meier estimated mortality rate in each treatment group at 180 days, the absolute difference between the assigned treatment groups at 180 days, and the 95% confidence interval for the difference will be presented. Transfusion strategy comparisons of the EQ-5D quality life measures at 30 days will be based on t-tests or the Wilcoxon rank sum test. No adjustment of the alpha level will be made for the secondary and tertiary analyses. Rather the results will be interpreted based upon the observed findings, their designation as secondary or tertiary outcomes, and in comparison to the primary outcome result.

The secondary outcomes include: 1) all-cause mortality within 30 days; 2) myocardial reinfarction within 30 days; and 3) the composite outcome of all-cause mortality, nonfatal myocardial reinfarction, ischemia driven unscheduled coronary revascularization (percutaneous coronary intervention or coronary artery bypass grafting), or readmission to the hospital for ischemic cardiac diagnosis within 30 days.

The tertiary outcomes include: 1) all-cause mortality, nonfatal myocardial reinfarction, and unstable angina (i.e. acute coronary syndrome) 2) ischemia driven unscheduled coronary revascularization within 30-days; 3) readmission to the hospital for ischemic cardiac diagnosis, 4) congestive heart failure within 30 days; 5) unscheduled readmission to hospital for any reason within 30 days; 6) each of the individual cardiovascular outcomes of stroke, pulmonary embolism or deep venous thrombosis, and bleeding within 30 days; 7) each of the individual infectious outcomes of pneumonia, blood stream, and urinary tract within 30 days; 8) each of the individual in-hospital outcomes of length of hospital stay post randomization and number of days in intensive care unit; 9) patient reported quality of life measures based on the EuroQol questionnaire (EQ-5D) at 30 days; and 10) all-cause mortality at 6-months.

4.e Missing Outcome Data

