Subgroup analyses will be performed based on baseline factors identified prior to the initiation of the trial. Clinically relevant subgroup variables include: ST segment elevation MI / non ST segment elevation MI, Universal Definition type 1 MI / type 2 MI, type 4b and 4c, baseline hemoglobin level (<8, 8-9, 9-10 g/dL), revascularization for treatment of index MI, bleeding, sex, race/ethnicity (White, Black, Other Race and Hispanic, non-Hispanic), age (<70, ≥70 years old), left ventricular dysfunction, diabetes status, and creatinine clearance (eGFR <30, 30-59, ≥ 60). The 30-day event rates by assigned transfusion strategy will be compared within each pre-defined subgroup. The reported significance-level will account for the number of treatment comparisons conducted in the study using the false discovery rate (FDR) algorithm developed by Benjamini and Hochberg. In addition, for each subgroup variable, a log-binomial regression model including treatment assignment, subgroup variable and the interaction between the subgroup variable and treatment assignment will be created, and the significance of the interaction term will be used to test whether the randomized treatment effect is significantly modified by the designated subgroup variable. Cox proportional hazards regression models will be created with similar covariates in order to test whether the effect of the randomized transfusion strategy for 6-month mortality varies significantly according to the prespecified subgroup variables.

4.g Combining Vanguard and Main Trial Data

In 2016, the Canadian Institutes of Health Research (CIHR) funded a MINT Pilot trial. This pilot is coordinated by the University of Montreal, and the clinical sites are in Canada. The DCC and CCC have collaborated with the University of Montreal to ensure that the protocol (eligibility criteria,

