### ***1. TRIAL DESIGN***

#### **Study Design**

The MINT trial is a randomized, open-label, multicenter clinical trial designed to determine whether a liberal transfusion strategy with a threshold of 10 g/dL reduces the composite outcome of all-cause mortality or nonfatal myocardial reinfarction through 30 days, compared with a restrictive transfusion strategy with a threshold of 7 to 8 g/dL among patients with an acute myocardial infarction and a hemoglobin concentration less than 10 g/dL. The trial is conducted in approximately 144 clinical sites in the United States, Canada, France, Brazil, New Zealand, and Australia. The two transfusion strategies are allocated with a 1:1 ratio using a permuted block design, with random variable block sizes, stratified by clinical site.

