## Primary Outcome Analysis

The primary endpoint (the composite of all-cause mortality and myocardial infarction (death/MI) by 30 days from randomization) will be compared by assigned transfusion strategy using an unadjusted log-binomial regression model with a fixed effect variable for assigned treatment strategy and a random effect for clinical site and accounting for missing data using multiple imputation to impute missing 30-day outcome data.

$$\text{Ln}(p_{ij}) = \beta_0 + \beta_1 \text{Restrictive}_{ij} + \alpha_i + \epsilon_{ij}$$

where  $p_{ij} = \text{Prob}(\text{Primary Endpoint} = 1 \mid \text{Participant Assigned Treatment and Site})$ ,

$i = \text{site}$ ,  $j = \text{participant}$ ;

$\alpha_i$  is the random intercept for site  $i$

We will present the estimated risk ratio, 95% CI and p-value for the Restrictive Strategy versus the Liberal Strategy based on this model. Markov Chain Monte Carlo (MCMC) multiple imputation methods will be used to impute the missing 30-day outcome values (yes/no) for death and MI based on all available observed data (baseline, in-hospital and 30-day variables). Ten imputed data sets will be created, a log-binomial model with random effects for site will be estimated for each imputed data set, and the results will be pooled to obtain a single estimate of treatment effect with an adjusted standard error. A log-binomial model with random effects for site will be created from patients with non-missing 30-day death/MI data as a sensitivity analysis. Also, if significant imbalances in baseline risk factors are detected between the two randomized treatment groups, a multivariable log-binomial regression model adjusting for the imbalanced factors will be created as a sensitivity analysis. If adherence to the protocol is a concern, a per protocol analysis, including only patients who undergo transfusion according to their assignment (and adjusting for baseline factors that are associated with adherence to the treatment protocol, will be conducted as a sensitivity analysis.

For each of these models, the primary hypothesis test will be a two-sided test with  $\alpha = 0.05$ :

$$H_0: \text{RR} = 1.00 \text{ versus } H_A: \text{RR} \neq 1.00 \text{ using a two-sided alpha-level} = 0.05$$

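### The subgroup interaction model omits the clinical-site random intercept used in the primary model, so its intervals are valid but slightly wider than they need to be

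*SAP*

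**What the plan says.** The SAP (Study Design) allocates patients "using a permuted block design, with random variable block sizes, stratified by clinical site". The primary model (SAP, Primary Outcome Analysis) has "a fixed effect variable for assigned treatment strategy and a random effect for clinical site", and its equation carries a site index and a site intercept.

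For subgroups the SAP (Subgroup Analyses) says that "a log-binomial regression model including subgroup variable, treatment assignment and the interaction between the subgroup variable and treatment assignment will be created". The equation below that sentence is indexed by participant only, and its probability is conditional on treatment and subgroup. Protocol F4 4.f lists the same terms: "a log-binomial regression model including treatment assignment, subgroup variable and the interaction between the subgroup variable and treatment assignment will be created". Neither document says why site is left out. The SAP sentence defines the interaction test. The sentence on the forest-plot risk ratios and intervals names no model. The SAP calls the subgroup analyses descriptive.

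For dichotomous secondary and tertiary outcomes, protocol F4 4.d gives risk ratios and intervals "using log-binomial regression methods accounting for clinical site with random effects". The SAP section on secondary and other outcomes says only that these quantities will be calculated and presented. It then uses the same 95% interval to declare non-inferiority when the interval lies wholly below 1.15.

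**The concern.** The same endpoint is modelled in two ways: with site in the primary analysis and without it in the subgroup analysis. When randomization is stratified on a factor related to outcome, leaving that factor out of the model keeps between-site variation in the residual. Standard errors then tend to be larger than the design requires.

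Two things are at stake, both modest. The subgroup intervals and interaction tests lose a little precision. For the secondary and tertiary outcomes, a formal non-inferiority statement rests on an interval whose model the SAP does not name, so the choice could be made after results are known.

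**Working it through.** **Inputs.** Event rates 18.2% and 14.6%, 3324 analyzable patients, two-sided alpha 0.05 (SAP section 4). ICC 0.05 to 0.08, with 60 sites of 56 patients (protocol F1). About 144 sites (SAP, Study Design), taken as 144 sites of 24. An ICC of 0.02 is my assumption, added to show the lower end.

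**1. The plan's own figure.** With 1662 per arm and pooled rate 0.164, SE under the null = √(2 × 0.164 × 0.836 / 1662) = 0.01284. SE under the alternative = √((0.182 × 0.818 + 0.146 × 0.854) / 1662) = 0.01283. Power = Φ((0.036 − 1.96 × 0.01284) / 0.01283) = Φ(0.844) = 80.1%. The stated 80% is reproduced. A chi-square without site at N = 3360 and alpha 0.045 gives 79.2%, against the protocol's simulated 81% with site.

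**2. Approximate size.** Removing between-site variance reduces the residual variance by a factor of about 1 − ICC, so the SE ratio (without site / with site) is about 1/√(1 − ICC): 1.026 at 0.05 and 1.043 at 0.08.

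**3. Simulation of the subgroup analysis.** Set-up: permuted blocks of 4 within site, liberal risk 14.6%, risk ratio 1.25, no true interaction, beta-distributed site risks, 2000 trials per setting. There were two subgroups of about half each, spread evenly over sites or clustered by site. Without site, the variance of the log risk ratio is 1/a₁ − 1/n₁ + 1/a₀ − 1/n₀, where a is events and n is patients per arm. Site adjustment was represented by the site-stratified Mantel-Haenszel risk ratio, Σ(a₁n₀/N) / Σ(a₀n₁/N), with its usual variance. Each cell shows even / clustered; coverage and type I error are in %.

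| Sites × patients | ICC | SE ratio | 95% CI coverage, no site | Coverage, with site | Interaction type I error, no site | Type I error, with site |
|---|---|---|---|---|---|---|
| 60 × 56 | 0.02 | 1.003 / 1.003 | 94.90 / 94.85 | 94.95 / 94.35 | 4.45 / 5.60 | 4.50 / 5.75 |
| 60 × 56 | 0.05 | 1.019 / 1.020 | 95.45 / 94.90 | 95.55 / 94.60 | 5.25 / 4.85 | 5.00 / 5.10 |
| 60 × 56 | 0.08 | 1.037 / 1.038 | 96.15 / 96.40 | 95.25 / 95.00 | 5.15 / 4.40 | 5.20 / 5.50 |
| 144 × 24 | 0.02 | 0.990 / 0.993 | 94.85 / 95.50 | 94.95 / 95.25 | 5.60 / 4.55 | 5.20 / 4.85 |
| 144 × 24 | 0.05 | 1.006 / 1.012 | 95.25 / 95.80 | 94.90 / 95.60 | 4.75 / 5.10 | 4.75 / 5.50 |
| 144 × 24 | 0.08 | 1.025 / 1.029 | 95.80 / 95.85 | 95.10 / 95.15 | 5.85 / 4.30 | 5.40 / 5.40 |

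Monte Carlo error is about √(0.05 × 0.95 / 2000) = 0.5 points. Bias in the log risk ratio without site was below 0.005 in every setting. At ICC 0.05 to 0.08 the SE without site is 0.6% to 3.8% larger.

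**4. The model actually proposed.** The random-intercept log-binomial interaction model was also fitted directly, in 150 simulated trials per setting at ICC 0.05 to 0.08 with both site layouts. Every fit gave usable standard errors, and the model without site had standard errors about 2% to 6% larger. Mantel-Haenszel weights sites less efficiently than the log-binomial likelihood, so a somewhat larger gain here is plausible. Together, steps 3 and 4 give roughly 1% to 6%.

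**5. What this means for the 1.15 rule.** As an illustration, take an outcome with primary-endpoint rates in the whole sample. In 1500 simulated trials (60 × 56, ICC 0.08) the mean SE was 0.0791 without site and 0.0760 with it. The largest observed risk ratio that passes is 1.15 / exp(1.96 × SE):
- without site: 1.15 / exp(0.1550) = 0.985
- with site: 1.15 / exp(0.1490) = 0.991

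Only results between these values would change status.

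**The case against.** Much of the case for leaving the plan as it is stands.

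- A reader might infer that the subgroup intervals use a wrong variance or are invalid. They are not: coverage without site is 94.9% to 96.4% at the protocol's ICC range, and interaction type I error is close to 5%.
- A reader might infer that subgroup estimates cannot be compared with the primary estimate. Treatment is balanced within site and the risk ratio is collapsible, so both models target the same quantity.
- A reader might infer that the SAP removed a term. For subgroups, protocol 4.f never had one. For secondary outcomes the SAP is silent, and its introduction says it is consistent with the protocol, so the protocol 4.d model can be read as still in force.
- The quoted sentence covers the interaction test. No document says that the forest-plot intervals are computed without site.
- Protocol F1 already reports comparable power for the random-intercept model and the chi-square at this ICC range. Simulated power in a half-sample subgroup changed by only about −1 to +4 points.

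The convergence objection is weaker. With 3500 / 144 ≈ 24 patients per site there are about 6 per site in an average category of a four-level subgroup, and separate fits by category could be fragile. The interaction model, however, uses all participants with subgroup data, and the direct fits in step 4 were all usable. Those fits used two subgroups of about half each, so some risk remains for rare outcomes and sparse categories.

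**Conclusion.** The omission is real, and its effect is small and conservative. At ICC 0.05 to 0.08, subgroup standard errors are roughly 1% to 6% larger than with site in the model. At an assumed ICC of 0.02 there is no gain. No bias or excess type I error was found. This is a minor consistency and efficiency point in a descriptive analysis.

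The part with most practical weight is the unnamed model for secondary and tertiary outcomes, because the non-inferiority rule depends on its interval. Even there, the zone in which the choice matters is narrow (0.985 to 0.991 in the illustration).

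The figures assume equal site sizes, blocks of 4, two subgroups of about half each, and no variation of the treatment effect between sites. A random intercept would not capture such variation either.

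A reader might also infer that the 6-month Cox subgroup models need a site frailty. The documents do not support that: the main 6-month analysis uses Kaplan-Meier estimates and a log-rank test with no site adjustment, so a frailty would create a mismatch.

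**What to change.** 1. In SAP Subgroup Analyses, replace the equation with Ln(p_ij) = b0 + b1 Subgroup + b2 Restrictive + b3 Subgroup×Restrictive + a_i, where a_i is the random intercept for site i.
2. State that the subgroup risk ratios and 95% intervals in Figures 4a and 4b are contrasts from this model.
3. In SAP Analysis of Secondary and Other Outcomes, restate the protocol 4.d log-binomial model with site random effects as the source of the risk ratios and intervals for the dichotomous secondary and tertiary outcomes, including the intervals used for the 1.15 rule.
4. State the fallback: use the model without site if the site variance is estimated as zero or the model does not converge, and report where this happened.
5. Leave the 6-month Cox subgroup models without a site frailty.

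The cost is a few lines of SAP text and a model term already needed for the primary analysis. No extra data or patients are required. The change should be made before results by arm are seen.
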